8.4.3. Electrocardiogram

The average of multiple values collected at one visit will be used for summarization, including baseline ECG values. For each ECG measurement (heart rate and PR, QRS, QT, and QTcF intervals), the observed value at each scheduled visit and change from baseline at each scheduled visit will be provided by treatment group. This summary will also include last values on treatment and on study. Last value on treatment is defined as the last post-baseline value between first dose of IP (exclusive) and up to last dose of IP + 1 days (inclusive). Last value on study is defined as the last post-baseline value after the first dose of IP.

In addition, the number and percentage of participants with PCS and potentially clinically significant change (PCSC) values will be summarized by visit/timepoint and for any time post-baseline. Potentially clinically significant values will be identified for ECG parameters as outlined in Table 13.

A shift table of overall ECG interpretation from baseline to scheduled post-baseline visits will be presented for the following categories: 'Normal', 'Abnormal, Not Clinically Significant', and 'Abnormal, Clinically Significant'. The shift table will be presented by visit and treatment group.

Clinically significant abnormal findings will be reported as adverse events. The average of the multiple values collected at one visit of each parameter will be listed by participant.

Units	Criteria for PCS Values (Observed Values)		Criteria for PCSC Values (Change from Baseline)	
	High	Low	Increase	Decrease
msec	 >450 msec and ≤480msec >480 msec and ≤500msec >500 msec 	NA	>30 msec and ≤60 msec >60 msec	NA

 Table 13: Potentially Clinically Significant Values for QTcF

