7.3. Treatment Assignment

This is a randomized, double-blind, placebo-controlled study. Participants will be randomized in a 1:1:1:1 ratio to treatment groups (15 mg, 30 mg, 60 mg SAGE-324, or placebo), stratified by baseline propranolol use.

SAGE-324 or matching placebo will be administered orally once daily, to be taken before bed, with a snack if bedtime is not within 2 hours of the evening meal.

The placebo dose group will receive matching placebo from Day 1 to Day 90.

The 15-mg SAGE-324 dose group will receive 15 mg of SAGE-324 from Day 1 to Day 90.

The 30-mg SAGE-324 dose group will receive 30 mg of SAGE-324 from Day 1 to Day 90.

The 60-mg SAGE-324 dose group will receive 15 mg of SAGE-324 from Day 1 to Day 14, then 30 mg from Day 15 to Day 28, then 45 mg from Day 29 to Day 42, and then 60 mg from Day 43 to Day 90.

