5. STUDY DESIGN

5.1. Overall Design

This study is a Phase 2, randomized, double-blind, placebo-controlled, dose-ranging study to evaluate the efficacy, safety, and tolerability of SAGE-324 in participants with ET. Participants, site staff, and sponsor personnel will be blinded to treatment allocations. This study includes a Screening Period of up to 28 days, a 90-day double-blind Treatment Period (90 days of dosing), and a 14-day Follow-up Period. See the Schedule of Assessments (Appendix A) for the full list of study assessments and timings. A schematic of the study is presented in Figure 1.

Participants who have provided informed consent will undergo screening assessments to determine eligibility. The Screening Period may be extended for an additional 14 days (to a total of 42 days) for subjects requiring additional time to taper ET medication (other than propranolol), after approval from the sponsor.

Following completion of screening and Day 1 eligibility assessments, participants will be randomly assigned to 1 of 4 treatment groups (placebo or SAGE-324: 15 mg, 30 mg, or 60 mg, oral daily) in a 1:1:1:1 ratio, stratified by baseline propranolol use (adjunct therapy).

The 15-mg dose group will receive 15 mg of SAGE-324 from Day 1 to Day 90.

The 30-mg dose group will receive 30 mg of SAGE-324 from Day 1 to Day 90.

The 60-mg dose group will receive 15 mg of SAGE-324 from Day 1 to Day 14, then 30 mg from Day 15 to Day 28, then 45 mg from Day 29 to Day 42, and then 60 mg from Day 43 to Day 90.

Starting on Day 1, after randomization, participants will receive a single dose of IP once daily for 90 days on an outpatient basis, to be taken before bed, with a snack if bedtime is not within 2 hours of the evening meal. During the Treatment Period, participants will return to the study center for efficacy and safety assessments as specified in Appendix A.

Follow-up visits will be conducted on an outpatient basis on Days 97 and 104. Participants will continue to complete questionnaires as indicated in Appendix A and will return to the clinic approximately 6 days after the last dose of IP (ie, Day 97) for efficacy and safety monitoring. Participants will return to the study center for an End of Study (EOS) visit approximately 13 days following the last dose of IP (ie, Day 104); the EOS visit will be conducted at the time of discontinuation if this occurs any time before Day 104.

No dose reductions of SAGE-324 will be permitted.

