7.2.2. Per Protocol Set

The Per Protocol Set will include all participants in the Full Analysis Set without any major protocol deviations that could affect efficacy. The review of major protocol deviations will be completed and the decision on whether the deviation affects efficacy and results in removal of a participant from the Per Protocol Set will be documented before database unblinding. The Per Protocol Set will exclude full analysis set participants satisfying any of the following conditions:

- Study Drug Adherence (defined in Section 8.2.7) < 75%
- Inappropriate drug consumption (typically due to incorrect kit dispensation): if the participant consumed at any time during the study any study drug that the participant is not randomized to
- Day 91 efficacy assessment done 3 days or more after the last dose
- Essential tremor duration of less than 3 years
- Prohibited essential tremor medication during the treatment phase of the study (after completing the treatment is fine)
- Any other major protocol deviations that the protocol deviation review committee (PDRC) documents as impacting the primary efficacy analysis prior to the database lock.

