8.2.6. Investigational Product Exposure

Total drug exposure (in mg) is defined as the total IP in mg for SAGE-324 that was taken during the study. Total drug exposure for participants randomized to placebo is zero unless the participant has taken SAGE-324 by mistake, in which case the total drug exposure comes from SAGE-324 exposure. If a participant skips a dose on any of the days, the dose taken is 0 mg.

Total exposure duration to IP (in days) is defined as (date of last dose – date of first dose + 1). Note that this does not exclude days when the dose has been missed.

For participants that have been dispensed with SAGE-324 15mg, 30mg, and 45mg prepacked kit, but do not take the full 4 tablets, from a safety perspective, the general rule is that the tablets taken are assumed to be the active tablet(s) in the dispensed kit before counting any placebo tablets. For example, for a 15mg pre-packed kit, if the patient takes only one tablet, the tablet would be the 15mg tablet. If the patient takes 2 tablets, it would be assumed that they took the one 15mg tablet and one placebo tablet.

Planned exposure for the participants who complete the treatment period is defined as follows:

- 1. For participants randomized to the SAGE-324 15 mg group, 90 days of treatment times 15 mg
- 2. For participants randomized to the SAGE-324 30 mg group, 90 days of treatment times 30 mg
- 3. For participants randomized to the SAGE-324 60 mg group, the sum of 14 days of treatment times 15 mg, 14 days of treatment times 30 mg, 14 days of treatment times 45 mg, and 48 days of treatment times 60 mg

Planned exposure for the participants who discontinue the treatment period early is defined as follows:

1. For participants randomized to the SAGE-324 15 mg group, total exposure duration times 15 mg

Statistical Analysis Plan Methods Version 1.0 17-Jun-2024 Protocol Number: 324-ETD-202 (Version 6.0 2 November 2023)

- 2. For participants randomized to the SAGE-324 30 mg group, total exposure duration times 30 mg
- 3. For participants randomized to the SAGE-324 60 mg treatment group
 - If 1 ≤ total exposure duration ≤ 14, then planned exposure = total exposure duration times 15 mg
 - If 15 ≤ total exposure duration ≤ 28, then planned exposure = 14 days times 15 mg + (total exposure duration 14) times 30 mg
 - If 29≤ total exposure duration ≤ 42, then planned exposure = 14 days times 15 mg + 14 days times 30 mg + (total exposure duration 28) times 45 mg

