8.3.2. Visit Windows for Efficacy Analyses

The scheduled visits will not be windowed and will be used at nominal visit value for treatment and follow-up period visits (Day 1, Day 8, Day 15, Day 29, Day 43, Day 57, Day 71, Day 91, Day 97, Day 104). Unscheduled, end-of-treatment (EOT), and early termination visits (ETV) that happen on or before one day after the last dose will be mapped to a scheduled visit for analysis using the date of collection/assessment and Day 1, first dose date, as a basis to determine study day and then study day will be mapped to the intended visit according to the visit windows specified in the Table 2. Unscheduled, EOT, or ET visits that happen on or after 1 day after the last dose will be windowed using relative days since last dose date; the mapping will follow the visit window in Table 2. To accommodate as much data as possible into analysis, these windows have been widened relative to protocol-specified operational windows to have no gap between them; these windows are used for analysis purposes only.

Scheduled Visit	Study Day of Expected Visit	Study Day Window for Visit
Screening	Day -1	Days -28 to Day -1
Day 1 Predose	Day 1 Predose	Day 1 Predose
Day 8 (±1 day)	8	Day 1 Postdose to Day 11
Day 15 (±1 day)	15	Days 12 to 22
Day 29 (±1 day)	29	Days 23 to 36

Table 2:	Visit	Windows	for	Efficacy	Analy	vsis
				•		

Scheduled Visit	Study Day of Expected Visit	Study Day Window for Visit
Day 43 (±1 day)	43	Days 37 to 50
Day 57 (±3 days)	57	Days 51 to 64
Day 71 (±3 days)	71	Days 65 to 81
Day 91 (+1 day)	91	Days 82 to 96
Day 97/last dose +7 days (±3 days) 97/last dose+ 7 days		Days 97 to 100 (last dose+6 days, last dose + 10 days)
Day 104/last dose + 14 days $(\pm 3 \text{ days})(*)$	104/last dose + 14 days	≥ Day 101 (last dose + 11 days, last dose + 17 days)

Note: Parenthesized study days and study day windows are for unscheduled, EOT, and ET visits. For participants who have discontinued treatment prematurely with either unscheduled, EOT, or ET visits on or after 6 days of the last dose, those visits should be mapped to Day 97 or Day 104 using the parenthesized visit windows listed (ie, visit date – last dose date >1).

Note: (*) The scheduled visit of Day 104/last dose visit is for efficacy analysis excluding TETRAS.

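### The ECG 'last value on treatment' row ends one day before the Day 91 (+1) visit window does, so a compliant Day 92 ECG drops out of that row, usually in favour of Day 29

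*SAP*

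**What the plan says.** SAP 8.4.3 summarises each ECG parameter (heart rate, PR, QRS, QT, QTcF) by scheduled visit, as observed value and change from baseline. The same summary carries two further rows, the last value on treatment and the last value on study. A value counts as on treatment if it falls between "first dose of IP (exclusive) and up to last dose of IP + 1 days (inclusive". The last value on study is the last post-baseline value of any kind.

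The calendar around that rule is as follows.

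- **Dosing.** SAP 5.1: "participants will receive a single dose of IP once daily for 90 days on an outpatient basis, to be taken before bed". In the 60-mg arm (Protocol 7.3) the dose is 15 mg for the first two weeks and then rises in steps: "then 30 mg from Day 15 to Day 28, then 45 mg from Day 29 to Day 42, and then 60 mg from Day 43". The last of these steps runs through Day 90. SAP 8.2.6 counts "14 days of treatment times 45 mg, and 48 days of treatment times 60 mg" in the planned exposure of that arm.
- **ECG visits.** Protocol Table 2 and SAP Appendix A schedule ECGs at Screening, Day 1, Day 29 (±1), Day 91 (+1, EOT) and Day 104. SAP Table 6 repeats the one-day allowance at Day 91.
- **By-visit handling.** SAP 8.3.2, carried over to safety by SAP 8.4: "The scheduled visits will not be windowed and will be used at nominal visit value".
- **A neighbouring efficacy rule.** SAP 7.2.2 removes a participant from the Per Protocol Set for a "Day 91 efficacy assessment done 3 days or more after the last dose".

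**The concern.** The on-treatment limit is tied to the date of the last dose, and the visit window to the study day. If the last dose is on Day 90, the limit falls on Day 91 while the window runs to Day 92. A participant who follows the protocol can therefore have an EOT ECG that does not qualify for the row it was meant to supply.

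Missing the row by a day would matter little if another ECG had been taken shortly before. Here the previous scheduled ECG is about two months earlier. In the 15-mg and 30-mg arms that ECG is at least at the assigned dose. In the 60-mg arm it belongs to the titration phase. So the dose mismatch affects only the top-dose arm, and there the row labelled as the last on-treatment value could combine ECGs taken at 60 mg with ECGs taken at 30 mg. A change that grows with dose would look smaller in that row than it is.

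**Working it through.** **1. Reproduce the dosing calendar.** Planned days in the 60-mg arm (SAP 8.2.6): 14 + 14 + 14 + 48 = 90, so the last planned dose is on Day 90. SAP Table 2 agrees: it labels the follow-up visit "97/last dose +7 days", and 97 − 90 = 7. Its Day 104 label, last dose + 14, also fits: 104 − 90 = 14.

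**2. Apply the limit.** Limit = last dose + 1.

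| Last dose | EOT ECG | Days after last dose | Kept at + 1? | Kept at + 2? |
|---|---|---|---|---|
| Day 90 | Day 91 | 1 | yes | yes |
| Day 90 | Day 92 | 2 | no | yes |
| Day 89 (Day 90 missed) | Day 91 | 2 | no | yes |
| Day 89 (Day 90 missed) | Day 92 | 3 | no | no |

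**3. Find the fallback.** Day 104 lies beyond either limit. The only other scheduled post-dose ECG is Day 29 (±1). Dosing is at bedtime, so a daytime clinic ECG precedes that day's dose. For the 60-mg arm:

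| Day 29 visit held on | Days before a Day 90 last dose | Highest dose already taken | 60-mg doses already taken |
|---|---|---|---|
| Day 28 | 62 | 30 mg | 0 |
| Day 29 | 61 | 30 mg | 0 |
| Day 30 | 60 | 45 mg (one dose, by the calendar) | 0 |

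An EOT ECG on Day 91 or 92 follows all 48 planned 60-mg doses; the Day 29 ECG follows none. An unscheduled ECG between Day 30 and the limit would be used instead of Day 29.

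**4. Size, by assumption.** The documents do not say how many participants attend on Day 92 or miss the Day 90 dose. Assume a fraction f of 10% to 30%. The 60-mg arm is 26 monotherapy plus up to 14 adjunct participants, so about 40.

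- Participants whose row value comes from Day 29: 0.10 × 40 = 4, to 0.30 × 40 = 12.
- If an ECG effect were proportional to dose and still fully present two days after the last dose, the understatement of the arm mean in this row is f × (1 − 30/60): 0.10 × 0.5 = 5%, to 0.30 × 0.5 = 15%.

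**5. Sensitivity to the last-dose day.** Elsewhere SAP 5.1 places a follow-up visit "approximately 6 days after the last dose of IP (ie, Day 97", and the Day 104 visit about 13 days after the last dose. Taken literally these give 97 − 6 = 91 and 104 − 13 = 91. With a last dose on Day 91, a Day 92 ECG would be last dose + 1 and would be kept. The explicit dosing days, the exposure formula and SAP Table 2 all give Day 90, which is used here. The passages should be reconciled.

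**The case against.** The strongest reply is that almost nothing is lost. The row is a descriptive SAP addition: Protocol 13.6.5 asks only for ECG summaries by visit and QTcF values of potential clinical significance, and SAP 8.4 rules out hypothesis tests on safety data. Scheduled visits are analysed at their nominal day, so the Day 92 ECG still supplies the Day 91 line of the same table. It also stays in the shift table, in the by-visit and any-time counts of potentially clinically significant values and changes (PCS/PCSC), and in the listings. All of this stands. A reader might infer that the Day 92 ECG is discarded from the safety analysis, or that the ECG safety endpoint as a whole is understated; the documents support neither.

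A reader might also infer from SAP 7.2.2 that the SAP contradicts itself, because a Day 91 efficacy assessment two days after the last dose does not trigger that exclusion. That rule decides membership of an efficacy set and does not define on-treatment time for safety. It shows a different tolerance, not a contradiction. SAP 8.3.2 itself uses a one-day limit when it maps unscheduled, EOT and early-termination visits, so the + 1 in 8.4.3 has a parallel.

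That parallel does not answer the point. A one-day convention is workable in general, but here it is shorter than the window of the visit that is meant to supply the value, and the fallback is some 60 days earlier at a different dose. The last value on study does not fill the gap, since it is normally the Day 104 ECG, about 14 days off drug.

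The objection is also right that the size rests wholly on assumption and that the fallback to Day 29 is not automatic.

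**Conclusion.** The mismatch is real and confined to one descriptive row. For a Day 90 last dose, the on-treatment limit in SAP 8.4.3 is Day 91, while the permitted EOT window runs to Day 92. A compliant Day 92 ECG, or a Day 91 ECG after a missed Day 90 dose, is left out of the row. Absent an unscheduled ECG, the row then uses Day 29, which in the 60-mg arm normally follows only 30 mg or less, and never 60 mg.

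The row may therefore dilute a dose-related change in the top-dose arm. By how much is unknown. The 5–15% is an illustration that depends on the assumed 10–30% share, on dose proportionality, and on an effect that persists for two days after the last dose; none of these is in the documents. The calendar finding is firm if the last dose is on Day 90. Early discontinuers whose EOT ECG comes more than one day after their last dose meet the same rule. This is a small correction to a safety summary and does not threaten the ECG assessment as a whole.

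**What to change.** In SAP 8.4.3, make one of two changes.

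- **Extend the limit** to last dose + 2 days, inclusive. This changes one number and covers the whole Day 91 (+1) window after a Day 90 dose, as well as a Day 91 visit after a missed Day 90 dose. It does not cover a missed Day 90 dose combined with a Day 92 visit (last dose + 3), nor an early discontinuer whose EOT ECG is later than two days after the last dose.
- **Or tie the rule to the visit:** state that an ECG at the nominal Day 91/EOT visit, taken within that visit's window, counts as on treatment. This also covers the missed-dose-plus-Day-92 case. The sentence should say whether it applies only to participants who completed treatment, so that a Day 91 visit long after an early stop is not counted.

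The cost is that some ECGs taken two days after the last dose (three in the combined case under the second option) are labelled on treatment. No visit, dose or test changes. While editing, reconcile the approximate 6- and 13-day follow-up intervals with the Day 90 last dose. If the database is already locked, SAP section 2 requires the change to be documented and discussed in the clinical study report.

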8.4.4. Vital Signs

Vital sign results (systolic and diastolic blood pressure [mmHg], pulse pressure (mmHg), body temperature [°C], heart rate [beats per minute or bpm], and respiratory rate [breaths per minute]) and changes from baseline will be summarized by scheduled visit and treatment group. Pulse pressure is defined as [systolic blood pressure - diastolic blood pressure].

The average of multiple values collected at one visit will be used for summarization, including the Day 1 triplicates assessments of supine and standing blood pressure and heart rate.

Potentially clinically significant values will be identified for vital sign parameters as outlined in Table 14. For any post-baseline visit, potentially clinically significant values will be summarized by treatment group and visit.

The number and percentage of participants with orthostatic hypotension, defined as either a decrease in systolic blood pressure of ≥ 20 mmHg or a decrease in diastolic blood pressure of ≥ 10 mmHg from supine to standing position, will be summarized by treatment group at each visit. The PCS and orthostatic hypotension at baseline will be evaluated using the average of 3 triplicates.

Vital sign results will be listed by participant and timing of collection.

Any vital sign results considered clinically significant by the investigator will be captured as adverse events.

Vital Sign	Units	Criteria for PCS (Observed values)	Values)	Criteria f values (C Baseline	for PCSC hange from values)
		High	Low	Increase	Decrease
Heart rate (supine and standing)	Beats/min	>120	<40		
Systolic Blood Pressure (supine and standing)	mmHg	>180	<90	≥30	≥30
Diastolic Blood pressure (supine and standing)	mmHg	>110	<50	≥20	≥20
Supine - Standing Systolic Blood Pressure	mmHg	≥20			
Supine – Standing Diastolic Blood Pressure	mmHg	≥10			
Orthostatic hypotension: supine – standing SBP and	mmHg	$SBP \ge 20 \text{ and} \\ DBP \ge 10$			
DBP		$\begin{array}{c} \text{SBP} \geq 20 \text{ or } \text{DBP} \\ \geq 10 \end{array}$			

Table 14: Potentially Clinically Significant Values for Vital Sign Parameters

Sage Therapeutics, Inc. CONFIDENTIAL

8.4.5. **Physical Examination**

The occurrence of a physical examination and the date and time, along with the results of the mental status exam and the abbreviated neurological exam are collected. These will be presented in individual participant data listings only. After screening, any clinically significant abnormal findings in physical examinations will be reported as AEs.

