Once analysis visits are assigned based on the visit windows, all visits, including scheduled visits, unscheduled visits, and EOT/ETV visits, will be eligible for being flagged as the "analyzed record" within the analysis visit window; a participant's individual analysis visit window could potentially contain more than 1 visit. In the event of multiple visits falling within an analysis window or in case of a tie relative to number of days from the scheduled study day, the following rules will be used in sequence to determine the "analyzed record" for the analysis visit window:

- If data from the scheduled visit is available within treatment period, then the scheduled visit data will be used.
- If no data from the scheduled visit within treatment period is available, then the windowed visit data will be used.
- If more than one visit is in the same target day window, the data closest to the target day will be used.
 - If there is a tie with distance from visits to target day, the visit after the the target day will be used.

The summary by visit will use the "analyzed records" only – at most one per participant per visit. The data not flagged as the "analyzed record" will be included in listings. An unscheduled visit that does not fall under any analysis window (e.g. in case one is available after Day 107) will remain in the database and will be included in the listings.

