8.4. Safety Analysis

Safety and tolerability of SAGE-324 will be evaluated by stratum (monotherapy cohort and adjunct therapy cohort) and overall using incidence of TEAEs, vital signs, 12-lead ECGs, clinical laboratory evaluations. Safety data will be listed by participant and summarized for each treatment group and SAGE-324 overall.

For safety summary tables, apart from adverse events, the choice of visit records for summarization at a given visit will be following the same rules as described in Section 8.3.2. Additional visit window schedules required for 12-lead ECG and laboratory data (chemistry, hematology, urinalysis, coagulation) appear in Table 6 and Table 7.

Table 0. Visit W	Indows for 12-lead ECG	
Scheduled Visit	Study Day of Expected Visit	Study Day Window for Visit
Day 1	Day 1	Day ≤1
Day 29 (±1 day)	29	Days 2 to 60
Day 91 (+1 day)	91	Days 61 to 96
Day 104 (+3 days)	104	>Day 97 (> last dose + 6 days)

Table 6:	Visit Windows	for 12-lead ECG

Note: Parenthesized study days and study day window is for unscheduled, EOT, and ET visits. For participants who have discontinued treatment prematurely with either unscheduled, EOT, or ET visits on or after 6 days of the last dose, those visits should be mapped to Day 104 using the parenthesized visit window listed (ie, visit date – last dose date >1).

Scheduled Visit	Study Day of Expected Visit	Study Day Window for Visit
Screening	Day -1	Days -28 to Day -1
Day 1 Predose	Day 1 Predose	Day 1 Predose
Day 8 (±1 day)	8	Day 1 Postdose to Day 11
Day 15 (±1 day)	15	Days 12 to 22
Day 29 (±1 day)	29	Days 23 to 36
Day 43 (±1 day)	43	Days 37 to 50
Day 57 (±3 days)	57	Days 51 to 64
Day 71 (±3 days)	71	Days 64 to 81
Day 91 (+1 day)	91	Days 82 to 96
Day 104 (±3 days)	104	\geq Day 97 (\geq last dose + 6 days

Table 7:Visit Windows for Laboratory Data (Chemistry, Hematology, Urinalysis,
Coagulation)

Note: Parenthesized study days and study day window is for unscheduled, EOT, and ET visits. For participants who have discontinued treatment prematurely with either unscheduled, EOT, or ET visits on or after 6 days of the last dose, those visits should be mapped to Day 104 using the parenthesized visit window listed (ie, visit date – last dose date >1).

All safety summaries will be prepared using the Safety Analysis Set and treatment received. See Table 8 for details on how safety endpoints will be presented. No statistical hypothesis testing will be conducted on the safety data.

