8.4.2. Clinical Laboratory

All statistical analyses of laboratory values will be performed using SI units.

Some numeric lab values may be reported as '<n.n' or '>n.n'; these will be analyzed in the summary statistics as n.n/2 and n.n respectively. For example, triglycerides recorded as <0.50 mmol/L would be summarized as 0.25 mmol/L and potassium recorded as >6.0 mmol/L would be summarized as 6.0 mmol/L.

Continuous hematology (including coagulation), chemistry, and urinalysis results (raw and change from baseline) will be summarized by actual treatment group at each scheduled time point. Categorical urinalysis results will be summarized by frequencies and percentages at each scheduled timepoint. The number and percentage of participants with shift changes from baseline based on the laboratory normal ranges provided by the laboratory will be tabulated at each scheduled visit.

The number and percentage of participants with potentially clinically significant (PCS) values at any time after study drug administration (including unscheduled visits) will be summarized by treatment group for the hematology, chemistry and coagulation parameters defined in Table 9, Table 10, and Table 11, respectively.

Liver function tests will be monitored closely for potentially clinically significant values (Table 12) and will be summarized for occurrence any time post-baseline for these PCS thresholds (for conditions involving more than one parameter, the results need to be from the same timepoint).

Chemistry, hematology (including coagulation), and urinalysis data will be listed with the values outside the normal ranges flagged. Blood cell morphology and microscopy test results will be listed when available but not summarized. Pregnancy tests, and urine drugs of abuse data will be listed but not summarized.

Laboratory Parameter	Sex	Units	Criteria for PCS Val	ues (Observed values)
			High	Low
Hemoglobin	Male	g/L	>185	<115
	Female	g/L	>170	<100
Hematocrit	Male	Fraction of 1	>0.55	< 0.385
	Female	Fraction of 1	>0.49	< 0.345
Platelet count		10^9/L	>600	<125
White blood cell		10^9/L	>15	<2.5
Basophils		10^9/L	>0.5	NA
Eosinophils		10^9/L	>1.5	NA
Neutrophils		10^9/L	NA	<1.5
Lymphocytes		10^9/L	>6.0	<0.5
Monocytes		10^9/L	>1.4	NA

Table 9: Potentially Clinically Significant Values for Hematology

Laboratory Parameter	Units	Criteria for PCS Values (C	Observed values)
		High	Low
Albumin	g/L	>70	<28
Blood urea nitrogen	mmol/L	>10.71	NA

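### SAP 8.4.4 counts abnormal vital signs and orthostatic hypotension by visit only, without the any-time post-baseline count that labs and ECG have

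*SAP*

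**What the plan says.** SAP 8.4.4 covers potentially clinically significant (PCS) vital signs in one sentence: "For any post-baseline visit, potentially clinically significant values will be summarized by treatment group and visit". Orthostatic hypotension is a fall of at least 20 systolic or 10 diastolic "mmHg from supine to standing position, will be summarized by treatment group at each visit". Neither sentence mentions a count over the whole post-baseline period.

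Which reading stands for a visit is settled elsewhere. SAP 8.4 says that, for safety tables other than adverse events, "the choice of visit records for summarization at a given visit will be following the same rules as described in" Section 8.3.2. That section admits "at most one per participant per visit" to the by-visit summaries and ranks the candidates: "If data from the scheduled visit is available within treatment period, then the scheduled visit data will be used". Readings not chosen go to the listings.

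The two preceding sections go further. Under SAP 8.4.2, labs count participants with PCS values "at any time after study drug administration (including unscheduled visits"). Under SAP 8.4.3, ECG values are "summarized by visit/timepoint and for any time post-baseline".

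Protocol 13.6.4 says only that PCS vital signs are summarized by treatment. The table concerned, 14.3.4.6.2, appears in SAP Appendix D as a title without a shell.

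**The concern.** A safety reader's first question about blood pressure or heart rate is how many people in each arm ever crossed a threshold. The specified tables answer a different one: how many crossed it at each visit, judged on one selected reading. The SAP gives no reason for treating vital signs differently from labs and ECG.

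The selection rule matters because an extra blood pressure is often taken when a participant feels unwell. Protocol 5.2 names dizziness and somnolence among the most frequently reported events, and Protocol 12.1.4 calls for standing measurements at about 1 and 3 minutes. Orthostatic data are thus collected on purpose, and change from baseline in vital signs is a named safety endpoint. Safety is also to be shown by cohort. With up to 14 adjunct participants per arm, by-visit counts will be sparse and a per-participant count is easier to read.

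**Working it through.** The plan gives no figure to reproduce. The check compares the text, traces one reading through the rules, and then bounds what by-visit rows can show.

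**Step 1: the sections side by side**

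| Data | PCS count by visit | Any-time post-baseline count | Unscheduled visits named |
|---|---|---|---|
| Labs, SAP 8.4.2 | not stated | yes | yes |
| ECG, SAP 8.4.3 | yes | yes | no |
| Vital signs, SAP 8.4.4 | yes | not stated | no |
| Orthostatic hypotension, SAP 8.4.4 | yes | not stated | no |

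**Step 2: one reading through the rules**

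SAP Table 2 gives the Day 43 visit a window of Days 37 to 50. Take a participant on treatment who attends on Day 43 and has an unscheduled reading on Day 48.
- Both records fall in the same window. The scheduled one is used and the Day 48 reading goes to the listings.
- If the Day 43 visit is missed, the Day 48 reading becomes the analyzed record.

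The 60-mg arm shows why this can matter. Doses are taken before bed and 60 mg starts on Day 43, so a clinic reading on Day 43 itself precedes the first 60-mg dose, whereas the Day 48 reading follows it. The next scheduled vital signs are on Day 57.

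The on-treatment windows have no gaps, so for a participant who attends every visit an unscheduled reading normally shares a window with a scheduled one. The preference for scheduled data is worded for the treatment period, which covers seven of the nine visits (Days 8 to 91). For the two follow-up visits the text is less explicit, but the limit of one record still applies.

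**Step 3: what by-visit rows can show**

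Input from the Schedule of Assessments: post-baseline vital signs on Days 8, 15, 29, 43, 57, 71, 91, 97 and 104, so k = 9. Let p be the share of participants meeting a criterion at each visit, with everyone attending all nine. The values of p are assumptions; the documents give none.
- Smallest ever-affected share (the same people every time): p
- Largest (different people every time): min(1, 9p)
- If visits were independent: 1 − (1 − p)^9

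| Assumed p | Smallest | Largest | Independent visits |
|---|---|---|---|
| 2% | 2% | 9 × 2% = 18% | 1 − 0.98^9 = 16.6% |
| 5% | 5% | 9 × 5% = 45% | 1 − 0.95^9 = 37.0% |
| 10% | 10% | 9 × 10% = 90% | 1 − 0.90^9 = 61.3% |

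Identical by-visit tables can thus describe very different numbers of people. This holds even if no unscheduled reading is ever taken.

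**The case against.** A reader might infer that unscheduled vital signs are discarded and the number of people affected is lost. The documents do not support that.
- SAP 8.3.2 states that "all visits, including scheduled visits, unscheduled visits, and EOT/ETV visits, will be eligible for being flagged as the" analyzed record. An unscheduled reading is used when its window holds no scheduled one, for example after a missed visit.
- Every reading stays in Listing 16.2.8.4, so the ever-affected count can be worked out by hand. It is only absent from the tables.
- An any-time row is not ruled out. The opening of the 8.4.4 sentence is loose, Protocol 13.6.4 says only by treatment, the selection rule speaks of summaries at a given visit, and Table 14.3.4.6.2 has no shell. The row is unspecified, not refused.
- Only the lab section names unscheduled visits. The ECG section says any time post-baseline and stops there.
- Important readings have another route. Under SAP 8.4.4 those the investigator considers clinically significant become adverse events, and these are counted once per participant regardless of visit windows.
- Protocol 5.2 does not report hypotension or bradycardia, so linking dizziness to those readings is inference. The scheduled contacts between visits are phone calls without vital signs, so extra clinic readings may be few.

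All of this stands and limits the point, but it does not supply the missing count. Listings leave the counting to the reader. The adverse-event route depends on judgement, whereas the Table 14 thresholds are fixed, and Protocol 12.2.1 does not require separate reporting of vital-sign changes clearly attributable to another adverse event.

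**Conclusion.** The point holds in limited form. As specified, vital-sign PCS values and orthostatic hypotension are tabulated by visit only, from at most one record per participant per window. An unscheduled reading is left out of those tables whenever a scheduled one exists in its window, and the number of distinct participants ever affected cannot be read from them. Labs and ECG both have an any-time count.

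The size of the first effect is unknown, because the documents give no rate of unscheduled readings. The second is bounded by arithmetic: under the assumption of equal rates and full attendance, the ever-affected share can be anywhere from one to nine times the per-visit rate (capped at 100%).

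No hypothesis test rests on these tables, since SAP 8.4 plans none for safety data. This is an inexpensive improvement to reporting, not a flaw that threatens the trial's conclusions.

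**What to change.** Add to SAP 8.4.4 and Table 14.3.4.6.2 the number and percentage of participants who meet each Table 14 PCS or change-from-baseline (PCSC) criterion, and who have orthostatic hypotension, at any time post-baseline including unscheduled visits. Present it by treatment group and by cohort, as SAP 8.4 already requires for safety. Keep the by-visit rows, which show timing.

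The cost is one row per criterion in an existing table, from data already collected. The small downside is that unscheduled readings may be prompted by symptoms, so arms with more symptoms may be measured more often. A footnote should say so.
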